### 2.1.3 Clinical application

For intended examination, the detection of blood in the upper gastrointestinal tract, the patient swallows the HemoPill acute capsule (after activation) ((1) in Figure 2-9). The capsule must be taken with at least 100 ml water, which aids swallowing and promotes the suspension of blood. The HemoPill acute continuously sends measurement data which are received and recorded by the HemoPill Receiver ((2) in Figure 2-9). Measurement data are displayed on the HemoPill Receiver for interpretation by the user ((3) in Figure 2-9). After the data acquisition procedure, the data can be printed using the HemoPill Printer.

[figure not shown]

Figure 9: Operation principle of the HemoPill acute system

The HemoPill acute continuously send approx. 5 measured values per minute to the HemoPill Receiver. The duration of the measurement is approx. 9 hours from activation of the HemoPill acute. The values measured by the capsule are displayed numerically and as a curve diagram on the display of the HemoPill Receiver (Figure 2-10). Furthermore, the capsule ID, which is individual for each individual capsule, is shown on the display, ensuring an allocation to the patient. The capsule ID is indicated directly on the blister packaging of the capsule. The separately enclosed patient labels (four stickers) serve the document in the patient file and do also include the capsule ID.

The numerical display shows the maximum HI value ( $^{MAX}HI$ ) (see (1) in Figure 2-10) and the last measured value ( $^{LAST}HI$ ) (see (2) in Figure 2-10)). The respective measuring time is located below.  $^{LAST}HI$  is updated with each measured value received (about 5 times per minute).  $^{MAX}HI$  updates every minute during the first hour, after the first hour until the 9th hour about every 8 minutes. The  $^{MAX}HI$  value is also plotted as a curve over time (Figure 2-10). By pressing the information button (see (3) in Figure 2-10) information on interpreting the HI values are shown.

[figure not shown]

Figure 10: Information on the display of the HemoPill Receiver

For interpretation of the HI values the following procedure is recommended:

1. First, interpret the maximum HI value within 10 minutes from swallowing the HemoPill acute, see Table 3.
2. Then interpret, independently of this, the maximum HI value in the further course of the measurement ( $\geq 10$  minutes after swallowing), see Table 4.

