## 2.2.5 Clinical Data to Date

Publications of clinical data on the use of HemoPill in Europe is described in chapter 2.1. Prior to market entry in the EU, a clinical trial was conducted which is described in the following:

Ovesco conducted a prospective non-randomized, single-center, open-label study to investigate feasibility and safety of the HemoPill acute in patients with symptoms of UGIB. The primary aim of the study was to investigate feasibility and safety of the device in a clinical setting. All patients underwent endoscopy within 12 hours after capsule ingestion. Sensor data from the capsule within 10 minutes after ingestion were compared with endoscopic findings.

From April 2015 to February 2016, 30 consecutive patients with symptoms of acute UGIB were included.

Objective and clinical endpoints of the investigation were:

- Safety of the capsule
- Feasibility of bleeding detection
- Evaluation of threshold values for the sensor capsule data
- Sensitivity and specificity of the sensor capsule data

The clinical investigation population were patients with indications on esophagogastroduodenoscopy (ESG) and with suspected upper GI bleeding. Inclusion criteria were:

- Clinical suspicion based on anamnestic statements of clinical symptoms such as hematemesis, tarry stools/melena
- Alert and conscious patient
- Written informed consent
- Age  $\geq$  18 years and  $\leq$  80 years.

The capsule was swallowed by the patient and an external study receiver recorded the capsule sensor data for 4 consecutive hours. Patients underwent endoscopy within 12 hours after capsule ingestion. Afterwards, the endoscopic findings (endoscopy pictures and patient's endoscopy record) were compared to the sensor capsule data results. Capsule excretion was monitored for up to 4 days. If excretion was not recorded during that time, a follow up examination of the patient would have been conducted after 10 days.

30 consecutive patients with symptoms of acute UGIB were included; 28 were eligible for analysis. All together the HemoPill acute was found to be feasible and safe.

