## 4 Study Design and Endpoints

### 4.1 Description of Study Design

Patients are included according to the defined inclusion criteria and prepared for endoscopy. At the latest possible time before endoscopy, a HemoPill acute capsule is administered with a minimal amount of water. The HemoPill receiver is stored in a carrying bag. The transparent part of the bag over the display of the receiver is covered with tape. The LED light is left uncovered, so a successful signal transmission can be checked at any times. The investigator is unaware of the HemoPill acute measurement result until endoscopy has concluded. After a latency of minimum 20 minutes, maximum 60 minutes, endoscopy is performed as scheduled, identifying blood within the GI lumen, if present. A minimum latency is introduced to ensure HemoPill acute is able to make a measurement without interference from endoscopy, e.g., insufflation or endoscopic light.

The amount of blood identified in endoscopy is visually analyzed and pictures are taken. For the estimation of the amount of blood present in a patient, comparative images are provided. Assessment categories are:  $x < 20$  mL and  $x > 20$  mL. The detection threshold is introduced to provide a point of reference for the HemoPill acute detection rate.

Pathologies, if found, are treated as per clinical standard. HemoPill acute measurements regarding presence or absence of blood are put in relation to endoscopic findings.

Endoscopic images are further analyzed to determine the digestive state of the blood found as HemoPill acute is capable of detecting fresh blood or hematin. Blood digested to a point beyond hematin is no indicator for an acute bleeding pathology. The following foreseeable combination of events are described and allocated to “True Positive”, “False Positive”, “True Negative”, and “False Negative”.

- **True positive:**  
HemoPill acute measurement indicates presence of blood; Endoscopy identifies fresh blood or hematin in the GI lumen
- **False positive:**  
HemoPill acute measurement indicates presence of blood; Endoscopy does not identify fresh blood or hematin in the GI lumen.
- **True negative:**  
HemoPill acute measurement does not indicate presence of blood; Endoscopy does not identify fresh blood or hematin in the GI lumen in quantities  $> 20$  mL; Minimum latency of 20 minutes achieved.
- **False negative:**  

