### ***5.4 Strategies for Recruitment and Retention***

The patient may be recruited from both inpatient and outpatient setting. Patient will be identified by our gastroenterology inpatient consult team when a consult for upper gastrointestinal bleeding has been suspected on admission or by an outpatient provider that is part of the study when they see the patient in their perspective clinics. Patients for suspected upper GI bleed will be asked by a study member of his/her willingness to participate in the study. The target number for subject recruitment is 50. The study team will not be using Epic as part of the recruitment process.

All subjects will be recruited from the PI and sub-investigators' practices or under their care in the inpatient setting. Potential subjects will be approached at one of their clinic visits by the PI, sub-investigator or research coordinator. Potential subjects will be approached after suspicion of a GI bleed led to the scheduling of endoscopy. Patient will be consented prior to scheduled endoscopy and sedation. Time between approaching potential subjects and onset of study procedures may vary as this depends on the scheduling of endoscopy. Scheduling for endoscopy is influenced by, e.g., urgency of the patient's situation and availability. It is not influenced by willingness or unwillingness to participate in the study. No recruitment materials are needed for this process.

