### 10.4.2 Analysis of the Primary Efficacy Endpoint(s)

The original continues data level of the subject device, HemoPill acute, the so-called HI-value, is transformed during the study process by the investigator in dichotomous values, negative or positive for GI lumen bleeding, i.e. negative or positive output results (described in detail in section 2.1.2.2).

The qualitative visual data of the control product, the endoscopy, is also transformed during the study process by the investigator in dichotomous values, negative or positive for GI lumen bleeding, i.e. negative or positive output results (described in section 4.1).

After the study process the values of these two factors (HemoPill acute: negative or positive, endoscopy: negative or positive) are combined in a 2 x 2 contingency table with four possible results:

- True positive: HemoPill acute measurement positive; Endoscopy measurement positive
- False positive: HemoPill acute measurement positive; Endoscopy measurement negative
- True negative: HemoPill acute measurement negative; Endoscopy measurement negative
- False negative: HemoPill acute measurement negative; Endoscopy measurement positive

(for detailed description see section 4.1)

From this 2 x 2 contingency table the summary three test indices are calculated accuracy (ACC, = (TP + TN) / pop), sensitivity (true positive rate) and specificity (true negative rate).

The significance of these results will be analyzed using the  $\chi^2$  test, goodness-of-fit test of a 2 x 2 contingency table with two tailed p-value of  $\alpha \leq .05$ .

The data assumption of the  $\chi^2$  test, goodness-of-fit test, a required minimal expected cell size of 5, will be controlled. After the inference analysis the 95% confidence intervals of the test indices can be calculated. If either of both measurement results is missing for a patient, the whole subject is omitted from the data analysis.

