## 10.5 Sample Size

The study will enroll in total n = 50 participants:

- at least 43 eligible for statistical analyses
- plus 7 as highest expectable dropout count.

The required sample size of n = 43 was calculated for the planned  $\chi^2$  test for the test indices (accuracy, sensitivity and specificity). The calculation was based on the previous clinical study of Burk et al. (2021) which provide an accuracy of 75% (sensitivity of 100% and specificity of 63%) equaling an assumed effect size  $w = 0.62$ . The calculation was done with an a priori set  $\alpha$  error of .05 and a targeted power (1- $\beta$ ) equal or higher than .90.

Based on the previous studies dropout ratios between 2% (Burk et al., 2021) and 7% (Caca & Zimmermann, 2017) could be expected. By reason of clinical judgement, a maximal dropout ratio of 14% was assumed (which equals two times the maximal previous dropout ratio). An assumed maximal dropout of 14% equals 7 additional participants (when targeting at least 43 participants eligible for statistical analyses).

The targeted n = 43 also assures the required minimal expected cell size of 5 for a  $\chi^2$  test being applicable. The method of power analysis was an a priori required sample size computation with given  $\alpha$ , power and effect size. The power analysis was conducted with the computer program G\*Power 3.1 (Faul et al., 2009).

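### The capsule call is a maximum over a window with no stated end, so patients with different ingestion-to-endoscopy latencies are read with index tests of different length

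*Combined protocol and SAP*

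**What the plan says.** **The call.** Section 2.1.3 takes the maximum HI in the first 10 minutes, positive at 0.8 or more (Table 3). The second step is: "Then interpret, independently of this, the maximum HI value in the further course of the measurement". It is positive at 1.0 or more (Table 4), and no closing time is given. The capsule sends about 5 values per minute.

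**The time available.** Section 4.1: "After a latency of minimum 20 minutes, maximum 60 minutes, endoscopy is performed as scheduled". Sections 6.1.5 and 6.3.1 repeat these bounds. The Protocol Summary has data collected until endoscopy concludes.

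**The analysis.** Section 10.4.2 sends the reader to section 2.1.2.2 for the positive/negative rule. That section explains how HI is calculated, but gives neither a decision rule nor a time window. Sections 10.3, 10.4.8 and 10.4.9.2 plan no further dataset, subgroup or exploratory analysis. Section 10.4.9.1 lists a time point per subject, and no analysis uses it.

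**The negative definitions.** In section 4.1 the 20-minute minimum is a condition for true and false negatives, but not for true or false positives.

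**The concern.** One reading at or above the cut-off makes a patient positive, and it stays that way. A patient observed for longer has at least as many opportunities to cross. Two patients with the same gastric contents can therefore be classified differently because their endoscopies began at different times.

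The documents contain a route to a false crossing. Section 2.1.2.2 says that undiluted bile in an empty stomach can give an HI of about 1.0. That is the Table 4 cut-off, and Table 4 governs the window whose length varies.

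The open end also leaves unclear whether readings taken during endoscopy count. Section 4.1 introduces the minimum latency to keep insufflation and endoscopic light from interfering with the measurement, and it keeps the display covered until endoscopy is over. A maximum read off at that moment may include the readings that the latency was meant to keep out.

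The trial exists to supply accuracy parameters for interpreting the device (section 2.4.1). A sensitivity and a specificity without a stated read-out time are harder to interpret, and a window left open can be chosen after the data are seen.

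**Working it through.** **The plan's own figure.** Section 10.5 gives n = 43, with an alpha "error of .05 and a targeted power (1- $\beta$ ) equal or higher than .90".
- For 75% against 50% accuracy, w = √(0.25²/0.5 + 0.25²/0.5) = 0.50. The noncentrality is 43 × 0.25 = 10.75, and with 1 degree of freedom the power is 0.906. So 43 reproduces.
- With the stated w = 0.62, 43 reproduces only at 5 degrees of freedom (power 0.901). At 1 degree of freedom, 28 would be enough.
- Dropout: 43/(1 − 0.14) = 50.

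The present point does not rest on any of this, and n does not change.

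**Window length** (sections 2.1.3 and 4.1).
- First window: minutes 0 to 10, the same for everyone.
- Second window at 20-minute latency: 20 − 10 = 10 minutes, 10 × 5 = about 50 readings.
- Second window at 60-minute latency: 60 − 10 = 50 minutes, 50 × 5 = about 250 readings.

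The ratio is five in time and in readings. It is not five in the chance of crossing, because readings 12 seconds apart in one capsule are unlikely to be independent.

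**Direction.** For any patient, max over (10, 60] ≥ max over (10, 20]. Hence P(positive) at 60 minutes ≥ P(positive) at 20 minutes, with or without blood. Sensitivity and false-positive rate can each only stay level or rise.

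**Illustration of size.** The documents give no rate of false crossing after minute 10, so I assume a range. I start from 17% false positives in the first 10 minutes (1 − 0.83, section 2.2.5). With h the chance of a false crossing per further 10 minutes, the false-positive rate at latency T is 1 − 0.83 × (1 − h)^((T − 10)/10).

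| Assumed h | FP rate, all at 20 min | FP rate, all at 60 min |
|---|---|---|
| 0% | 17.0% | 17.0% |
| 2% | 18.7% | 25.0% |
| 5% | 21.2% | 35.8% |
| 10% | 25.3% | 51.0% |

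Nothing in the documents says which row applies. The columns compare the two ends of the permitted range, not a likely mix of patients.

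**Net effect on accuracy.** With prevalence π, change in accuracy = π × (gain in sensitivity) − (1 − π) × (rise in FP rate). Taking π = 1/3 (20 of 60 in the multicentre series in section 2.1), the two terms cancel when the gain in sensitivity is twice the rise in the FP rate. In the 2% row the rise is 6.3 points, so a sensitivity gain above 12.6 points would make the longer window more accurate and a smaller gain less accurate. Section 2.2.5 reports sensitivity 100% with a 95% interval of 54 to 100%, which does not settle whether there is room for such a gain.

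**The case against.** The strongest reply is that the protocol already controls latency. Section 4.1 asks for the capsule at the latest possible time before endoscopy, which pulls patients towards 20 minutes, and the range is bounded at 60. This stands in part: the spread is probably narrower than the limits suggest. But the plan neither fixes a read-out time nor reports the latency achieved by cell.

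A second reply is that cutting every recording at minute 20 departs from the recommended reading. Blood met at minute 30 and seen at endoscopy at minute 40 would become a false negative if above 20 mL. That is fair, and it is why the 20-minute read-out belongs in a sensitivity analysis and not in the primary table. A common read-out is feasible: in the sponsor's earlier trial, "Sensor data from the capsule within 10 minutes after ingestion were compared with endoscopic findings".

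Three stronger readings are tempting, and the documents do not support them.
- *Urgency confounds latency with bleeding.* Section 5.4 says "Scheduling for endoscopy is influenced by, e.g., urgency of the patient's situation and availability", but it is explaining the time from approaching a patient to the start of study procedures. Ingestion is then fitted to a slot already set. Nothing ties urgency to the interval from ingestion to endoscopy.
- *Specificity of 83% with a 10-minute read-out against 63% in the planning series shows the effect.* The 83% has an interval of 60 to 95%, which contains 63%. The 63% is 25/(25 + 15) = 62.5%, which counts 5 capsule-negative patients without endoscopy as true negatives and 4 capsule-positive patients without upper endoscopy as false positives. The patients and indications also differ.
- *Latency costs a known, large amount of specificity or power.* That needs a crossing rate with no source. Placing 63% at 40 minutes with a constant rate, for example, gives −ln(0.63)/40 = 0.01155 per minute and a specificity of exp(−0.01155 × 540) = 0.2% at 9 hours, which is irreconcilable with 63% in a series where recordings could last about that long.

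**Conclusion.** The point holds as a gap in the definition and analysis of the index test. The second read-out window has no end, its pre-endoscopy length may differ five-fold between patients (10 against 50 minutes), and the chance of a positive call cannot fall with latency. The accuracy estimate therefore mixes read-out lengths, and nothing planned would show whether that matters.

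The conclusion rests on the call being a maximum and on the permitted latency range, both stated in the protocol. It does not depend on any crossing rate. The size cannot be derived: it is zero if no reading crosses after minute 20, and the net effect on accuracy may be a loss or a gain. A reader might infer that the results could not be carried to another site. A range bounded at 40 minutes does not support that.

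**What to change.** In section 10.4.2:
1. Replace the reference to section 2.1.2.2 with Tables 3 and 4 as the rule for the capsule call.
2. End the primary read-out window at the start of endoscopy.
3. Pre-specify as a sensitivity analysis the same 2 x 2 table and indices using only readings from swallowing to minute 20, in patients who reached the 20-minute minimum latency. Count and report separately any patient scoped earlier.
4. Summarise ingestion-to-endoscopy latency for each of the four cells.

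The cost is protocol wording and a little more analysis. The receiver saves the values, and its maximum updates every minute in the first hour (sections 2.1.1.1 and 2.1.3), so the 20-minute call can be recovered from stored data once ingestion and endoscopy start times are recorded. The downside is that blood first met after minute 20 counts as negative, but only in the sensitivity table. Sample size, capsule administration and endoscopy scheduling stay as they are.

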## 2.2.2 Device Category

The subject device is currently part of a DeNovo classification request. Thus, the specific device category is not yet established. If the DeNovo request is granted, a product code is assigned.

### 2.2.3 Non-significant risk rationale

Under 21 CFR 812.3(m), a significant risk device means an investigational device that:

- Is intended as an implant and presents a potential for serious risk to the health, safety, or welfare of a subject.

NSR Rationale: The subject device is not an implant.

- Is purported or represented to be for use supporting or sustaining human life and presents a potential for serious risk to the health, safety, or welfare of a subject.

NSR Rationale: The subject device is not intended for supporting or sustaining human life.

- Is for use of substantial importance in diagnosing, curing, mitigating, or treating disease, or otherwise preventing impairment of human health and presents a potential for serious risk to health, safety, or welfare of a subject

NSR Rationale: Within the context of this clinical trial, any eligible trial participant is already scheduled for endoscopy based on the individual clinical presentation. The HemoPill acute is ingested prior to endoscopy and does not disrupt the clinical course of the trial participant. HemoPill acute data is retrospectively analyzed and compared to endoscopic findings. The data is however not used for risk stratification and does not influence the further clinical course of a given trial participant. The subject device is therefore not of substantial importance in diagnosing, curing, mitigating, or treating disease. The subject device does not further prevent impairment of human health and does not present a potential for serious risk to health, safety, or welfare of a subject.

- Otherwise presents a potential for serious risk to the health, safety, or welfare of a subject.

NSR Rationale: The subject device does not present a serious risk to the health, safety, or welfare of a subject. Results from prior studies are provided in chapter 2.1. The described publications report on a total of 65 patients. Within these publications, no HemoPill acute capsule related complications were reported. One patient described discomfort while swallowing the HemoPill acute capsule (Brunk T et al., 2021).

### 2.2.4 Preclinical Data

Ovesco performed various bench tests on the HemoPill acute which are briefly described in Table 7.

Ovesco further conducted a volunteer trial and animal testing to investigate HemoPill performance. These are described in the following in more detail:

#### 2.2.4.1 Volunteer trial

Prior to market entry in Europe, feasibility testing was performed in a volunteer trial to evaluate the following aspects (Table 5):

Table 5: Aspects and acceptance criteria of the volunteer trial

No.	Aspect	Acceptance criteria
1	Direct, reproducible proof of presence of blood in stomach	The measures sensor value during the course of the test must react specifically and sensitively to the presence of blood
2	Quasi-continuous collection of measurement data	Data transmission from the capsule to the receiver unit must be quasi-continuous at a measurement frequency > 1/min.

No.	Aspect	Acceptance criteria
3	Operating time	The passage duration and therefore the operating time of the capsule must be at least 4 hours.
4	Introduction of capsule by swallowing	Capsule must be able to be swallowed without any problems.

The aspects described in Table 5 were investigated through a series of 8 tests. Before testing started the test subject had an empty stomach (no ingestion of food or drink in at least 4 hours before start of the test). Three different meal scenarios ((1) empty stomach, (2) breakfast, (3) dinner) were planned and the capsule was swallowed a few minutes after the respective meal and blood ingestion (with different concentrations). The dose of blood ingested consisted of autologous blood from the vein of the respective test subject. No additives were added to the blood, which was ingested immediately after it was drawn.

The data was acquired over the time period from the swallowing of the capsule to its expulsion.

